## **1.0 STUDY SYNOPSIS**

Study Title	A Prospective, Multicenter Study Comparing Healing After Treatment with the Sonendo GentleWave™ System as Compared to a Traditional Root Canal Therapy Literature Control (SUPREME)
Study Short Title	The SUPREME Study
Purpose	The purpose of this study is to assess healing rates following root canal therapy with the Sonendo GentleWave System as compared to a literature control.
Objective	The objective of this study is to evaluate healing and post procedure pain following root canal therapy (RCT) of 1 st and 2 nd molars treated with the Sonendo GentleWave System and to compare it to data presented in a traditional RCT literature control.
Sites	Up to 8 clinical sites in the United States
Study Design	A prospective, non-significant risk device, literature controlled, study evaluating healing rates for the Sonendo GentleWave System in the treatment of 1 st and 2 nd molars indicated for root canal therapy.
	All patients will receive root canal therapy with the Sonendo GentleWave System. All patients will be followed for 24 months post procedure.
Study Population	Up to 120 subjects, aged 18 to 75 years, who have a 1 st or 2 nd molar tooth indicated for root canal therapy, will be enrolled in the study.
Study Duration	Duration of 24 months
	Study Visits: Screening, Baseline, Treatment (within 7 days of Baseline) and 6, 12, 18, and 24 months.
	Expected Enrollment Commencement: August 2014
	Expected Enrollment Period: January 2016
	Expected Study Completion: March 2018
Sample Size	86 subjects
	Roll-in patients: Up to 5 per site
	Lost- to Follow-up 20%: 18 Subjects
	Total: Up to 120 patients
Roll-In Subjects	Roll-in subjects, up to 5 per clinical site, will be included in the study. The Sponsor will determine the required number of Roll-In cases depending on the Investigator's experience with the Sonendo

	GentleWave System and training. Roll-in cases may not be included in the final data analysis.
Study Cohorts	There will be two cohorts within the study. The two cohorts are defined as follows:
	All subjects meeting the Treatment Complete criteria
	All subjects meeting the Treatment Incomplete criteria
	Only subjects in the Treatment Complete Cohort will be followed for 24 months according to the study visit schedule. Only subjects in the Treatment Complete cohort will be included in the primary effectiveness and safety endpoint analyses.
Treatment Complete	Treatment Complete is defined as any subject that received 100% of the Sonendo GentleWave Treatment (Treatment) over the course of no more than two visits.
Definition of Sonendo GentleWave System Treatment	The Sonendo GentleWave System Treatment is defined as beginning when LuxaBite ® (DMG) or a Sonendo Tooth Cap is placed until 100% completion of the Sonendo GentleWave System. All other procedures will be categorized as traditional RCT procedures.
Indication	The Sonendo GentleWave System is intended to prepare, clean, and irrigate 1 st and 2 nd molar teeth indicated for root canal therapy.
Primary Effectiveness Endpoint	Subject teeth in the Treatment Complete cohort that are healed or are healing at the twenty-four month follow-up visit.
	Healed is defined by absence of a radiographic indication of apical periodontitis (PAI <3) and absence of clinical signs and symptoms.
	Healing is defined by a reduction of radiolucency (if radiolucency is present at Baseline) and/or reduction of clinical signs and symptoms (if clinical signs and symptoms are present at Baseline)
	Secondary analysis will be completed after all Treatment Complete subjects complete the 12 month follow-up. Additional analysis may occur.
Primary Safety Endpoint	Incidence of device related adverse events as defined by perforation, instrument separation, root fracture, sodium hypochlorite accident, or Gutta Percha extrusion, as related to the device for the Treatment Complete cohort.

Secondary Endpoint(s)	The following outcomes will be assessed:
	1. McGill Short Form Pain Questionnaire
	2. Gracely Descriptor Differential Scale (DDS)
	3. Patient Satisfaction Survey
	4. AAE Case Difficulty Assessment
	5. Soft Tissue Lesions
	6. Swelling
	7. Root Canal Therapy Retreatment
	8. Treatment Time
	9. Procedure Time
	10. Periapical Index (PAI) analyzed utilizing
	radiographic analysis by independent reviewer
	11. Cone Beam Computed Tomography (CBCT) Sub-Set Evaluation
	12. Additional Radiographic Analysis may be completed
Pre-Procedure Inclusion	1. The patient is 18 to 75 years of age
Criteria	2. The subject tooth is indicated for root canal therapy
	3. The subject tooth is a 1 st or 2 nd molar
	4. The patient is mentally and physically able and willing to fully comply with this protocol, including adhering to the follow-up schedule and completing forms and questionnaires
	5. Signed Informed Consent Form
Pre-Procedure Exclusion	1. Poor oral hygiene according to a Poor, Fair, Good Scale
Criteria	Poor: There is evidence of: generalized inflammation and
	swelling of gingival tissue, generalized bleeding on probing
	and/or generalized plaque/calculus accumulation
	2. Subject tooth with $\geq$ Class II Mobility
	3. Subject tooth with Periodontal Pocket Depth $\ge 6$
	4. Periodontal probe reaches the apex of the subject tooth
	5. Furcation involvement originating from periodontal disease, on the subject tooth, one or two adjacent teeth in direct contact with the subject tooth

6.	Subject tooth with $\geq$ Class III endodontic furcation involvement
7.	Subject tooth with open or incompletely formed root apices
8.	Vertical fracture, horizontal fracture, or perforation extending below the Cemento-Enamel Junction (CEJ) of the subject tooth
9.	Caries or another condition of the subject tooth that
	a. prevents adequate seal of the device
	b. requires a separate procedure for crown lengthening
	c. requires a post
	d. provides inadequate biological width for crown retention
10	Any dental treatment on the subject tooth completed with the known use of devitalizers or formocresol
11	. Subject tooth having previous or attempted pulpectomy or root canal therapy
12	. One or two adjacent teeth in direct contact with the subject tooth requiring root canal therapy, pulpectomy or pulpotomy
13	. Any tooth on the same side of the oral cavity as the subject tooth with a source of pain
14	. Extraoral swelling on or around the subject tooth that has not undergone antibiotic treatment or a procedure to treat the swelling prior to RCT
15	Any condition that would preclude tolerance of a root canal therapy including but not limited to being in a reclined and prolonged position in a dental chair, use of a dental dam, or ability to have an open mouth for extended periods of time (>15 minutes) (e.g. history of seizure within the last 5 years, severe asthma, or extreme gag reflex)
16	Any other condition that the Investigator determines is unacceptable for enrollment into the study
17	. Nonodontogenic facial pain
18	. History of cancer within the oro-maxillofacial region
19	. History of any cancer within the last two years, including skin cancer
20	. History of head and/or neck radiation therapy

	21. Immunocompromised patients (i.e. corticosteroid usage)
	22. Any medical history that affects blood coagulation (e.g. bleeding disorders)
	23. Long-term or current usage of medication that affects blood coagulation. This includes herbal or other over the counter medications. Exception: Patients taking daily low dose Aspirin (81mg) or patients that can stop Aspirin or Ibuprofen products three (3) days prior to procedure, should not be excluded from the study.
	24. Patients with any medical condition causing chronic pain (e.g. spinal injury)
	25. Patients on long-term (i.e. more than three months) narcotic, opioid, or other similar analgesic (e.g. daily narcotic pain medication for spinal disease)
	26. Any infectious diseases (e.g. HIV, Hepatitis B, Hepatitis C, Tuberculosis, BCE, or Prion diseases)
	27. Uncontrolled diabetes or diabetics with unknown hemoglobin A1c levels
	28. A known allergy to local anesthetics, titanium carbon-nitride or stainless steel
	29. A pacemaker, implantable cardiac defibrillator (ICD), or other implanted electronic medical device
	30. Patient is institutionalized, a prisoner, homeless, or on active military duty
	31. Patients with documented current alcohol and/or drug abuse
	32. Patient is pregnant or planning to become pregnant within the duration of the study
	33. Participated in any clinical study in the past 30 days
Intra-Procedure Inclusion	1. Successful removal of caries on the subject tooth
Criteria	
 
Successful completion of build-up to restore the subject tooth crown when used in combination with the Occlusal Plate. Exception: This does not apply when the Tooth Cap is utilized.
 

Intra-Procedure Exclusion	1. Use of laser devices
Criteria	2. Subject tooth that requires crown lengthening

	3. Subject tooth that requires a post
	
 
Subject tooth that provides inadequate biological width for crown retention
 

	5. Perforation of the subject tooth
	6. Vertical fracture or horizontal fracture below the Cemento- Enamel Junction (CEJ) of the subject tooth
	
 
Internal or external root resorption that affects the use of Sonendo GentleWave System
 

Assessments Completed for the Study	Data will be collected on the following Standard of Care Assessments:
	Medical and Dental History and Exam
	Medication Regime
	• Periapical Radiographs: PA Parallel Periapical Index (PAI) Scoring by an independent reviewer
	
 
General Dental Assessments including Tooth Number, Oral Hygiene, Probing Pocket Depth, Mobility Assessment, Swelling, Soft Tissue Lesions and Furcation Involvement
 

	
 
Endodontic Assessments including Periradicular Tests (Percussion and Palpation), Cold Test, Root Resorption, Pulp Diagnosis, and Periradicular Diagnosis
 

	
 
Procedural details including Calcification Assessment, Irrigation, and Material Utilization
 

	Sonendo GentleWave System Devices Utilized
	Traditional Root Canal Therapy Devices and Instruments Utilized
	Procedure Time (dental dam placement to removal)
	Sonendo GentleWave Treatment Time (Treatment Time)
	Cone Beam Computed Tomography (CBCT) Sub-Set Evaluation
	Radiographic Evaluation of Obturation
	Adverse Events
Questionnaires	The following questionnaires will be completed for the study:
Completed for the Study	
 
McGill Short Form Pain Questionnaire at Baseline, 1, 2, 3, 7 and 14 days post-procedure, at all Follow-up Visits and at Unscheduled Visits, as necessary
 

•	Gracely Descriptor Differential Scale (DDS) at Baseline, immediately post procedure and 1 day post procedure
•	Patient Satisfaction Survey immediately post procedure
•	AAE Case Difficulty Assessment post procedure

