#### 5.0 STUDY POPULATION

Up to 120 subjects, aged 18 to 75 years, who have a 1st or 2nd molar tooth indicated for root canal therapy, will be enrolled in the study.

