## 13.1 Sample Size

All patients will receive root canal therapy with the Sonendo GentleWave System and will be subsequently followed for 24 months post procedure. A sample size of 108 subjects, assuming a 20% lost to follow-up or Treatment Incomplete Cohort rate, will result in approximately 86 subjects who would be evaluable for the primary efficacy endpoint. A sample size of 86 evauable subjects provides approximately 90% power to detect a difference between a 85% response rate for subjects using the Sonendo GentleWave System against a null hypothesis of a 70% response rate based on data presented in literature for traditional root canal therapy, using a two-sided binomial test at the 5% level of significance.

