# **13.2** Analysis Populations and Handling of Dropouts

The Safety Population is defined as all patients who receive the Sonendo GentleWave System procedure.

The Efficacy Evaluable population is defined as all subjects who enroll in the study and who receive 100% of the Sonendo GentleWave Treatment (Treatment Complete Cohort) over the course of no more than two visits. Analysis of efficacy data will be performed using the Efficacy Evaluable population. Efficacy analyses will be based on observed data only; no imputation methods will be used. Dropout subjects will not be replaced.

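### Sample-size figures disagree between the synopsis and section 13.1, the 120 cap has room for only 12 roll-ins beside 108 subjects, and the protocol does not fix whether roll-ins are analysed

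*Combined protocol and SAP*

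**What the plan says.** **Size.** The Sample Size row of the synopsis lists 86 subjects, "Roll-in patients: Up to 5 per site", "Lost- to Follow-up 20%: 18 Subjects" and "Total: Up to 120 patients". The Sites row gives "Up to 8 clinical sites in the United States". Section 5.0 repeats the cap as "Up to 120 subjects, aged 18 to 75 years". Section 13.1 states: "A sample size of 108 subjects, assuming a 20% lost to follow-up or Treatment Incomplete Cohort rate, will result in approximately 86 subjects". It attaches approximately 90% power to those 86, for 85% against a null of 70% with a two-sided 5% binomial test. Sections 19.0 and 19.1 count the five roll-ins per PI, not per site.

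**Analysis set.** Section 13.2 reads: "The Efficacy Evaluable population is defined as all subjects who enroll in the study and who receive 100% of the Sonendo GentleWave Treatment" over no more than two visits. It makes no exception for roll-ins, and section 7.6.2 describes roll-ins as enrolled subjects with their own ID series. The synopsis says "Roll-in cases may not be included in the final data analysis", and section 19.1 says much the same. Sections 19.0 and 19.1 also let the sponsor choose to disregard one to five roll-in cases for a given PI. Section 13.0 leaves details of the analysis methods to a statistical analysis plan, which is not in the supplied text.

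**The concern.** The synopsis and section 13.1 cannot both be right about how many subjects to enrol for 86 evaluable. No section limits roll-ins to the number that the cap can absorb if they are excluded. The promised evaluable number and power therefore depend on a roll-in count that is left open.

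The more serious matter is membership of the primary analysis set. Read literally, 13.2 includes roll-ins, while other sections allow or require leaving them out. The synopsis sentence can be read as a prohibition or as an option. The sponsor's power to disregard cases can mean waiving training cases for an experienced PI, or dropping treated cases from the analysis.

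The study has one arm, is unblinded and is compared with a fixed literature rate. PAI readers are blinded (7.4.4, 7.17.2), but source documents and significant follow-up findings go to the sponsor after visits (7.17.2). A choice made late could thus be made with outcomes in view. Nothing in the protocol says that selection would use outcomes. The difficulty is that nothing excludes it, and a reader of the results could not verify that it did not happen.

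**Working it through.** **Reproducing section 13.1.** 86 / 0.80 = 107.5, so 108 enrolled. For n = 86, null 0.70, alternative 0.85 and at most 2.5% in the upper tail, the exact rule is 69 or more responders. Its upper-tail error is 0.0223 and its power 0.914. Section 13.1 is internally correct.

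**Synopsis against 13.1.** 108 − 86 = 22, not 18. The synopsis gives 86 + 18 = 104. The 18 matches 20% of 86 (17.2) rounded up, that is, 20% taken of the evaluable number and not of the enrolled number. With 104 enrolled, 104 × 0.80 = 83.2, about 83 evaluable: rule 67 or more, power 0.891.

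**Room under the cap.** 120 − 108 = 12 places. Permitted roll-ins: 5 × 8 = 40.

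**Power if roll-ins are excluded** (120 enrolled including roll-ins, 20% loss, evaluable = (120 − r) × 0.80):

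| Roll-ins r | Evaluable | Responders needed | Exact power |
|---|---|---|---|
| 12 | 86.4, about 86 | 69 | 0.914 |
| 16 (2 per site) | 83.2, about 83 | 67 | 0.891 |
| 20 | 80 | 65 | 0.862 |
| 24 (3 per site) | 76.8, taken as 76 | 62 | 0.841 |
| 40 (5 per site) | 64 | 53 | 0.754 |

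If all roll-ins are analysed: 120 × 0.80 = 96 evaluable, rule 77 or more, power 0.923. Exact power is not smooth in n.

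**Loss that still leaves 86**, from 1 − 86 / (120 − r): 20.4% at r = 12, 14.0% at r = 20, 4.4% at r = 30 and 0% at r = 34. Above 34 roll-ins, 86 is out of reach even with no loss.

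**Upper-tail error at a true rate of 70%** (nominal limit 2.5%), by exact enumeration. Each case is written as evaluable non-roll-ins plus evaluable roll-ins, and the most favourable permitted choice is taken after outcomes are known.

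| What may be chosen | Case | Error |
|---|---|---|
| All roll-ins in or all out | 86 + 10 | 2.56% |
| | 80 + 16 | 2.29% |
| | 72 + 24 | 2.40% |
| | 64 + 32 | 2.45% |
| Each PI's whole set in or out | 86 + 2 PIs × 5 | 2.84% |
| | 80 + 4 × 4 | 3.28% |
| | 86 + 5 × 2 | 4.08% |
| | 64 + 8 × 4 | 6.45% |
| | 72 + 8 × 3 | 6.72% |
| Each failing roll-in dropped (worst-case bound) | 86 + 10 | 4.96% |
| | 80 + 16 | 8.60% |
| | 64 + 32 | 30.3% |

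The first block applies if disregarding means waiving training cases, so that only an all-in or all-out choice remains. The other two apply only if treated cases can be dropped after outcomes are seen.

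**The case against.** The arithmetic is not in dispute; the weight is. The difference between 18 and 22 is close to clerical, and 89% power is still approximately 90%. The two rows also carry different labels: the synopsis counts loss to follow-up only, while 13.1 adds Treatment Incomplete.

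The figures 5, 8 and 120 are ceilings, and the sponsor sets the roll-in number by experience, so 12 against 40 is not a strict contradiction. Power falls only if more than 12 roll-ins are enrolled, they are excluded, and loss reaches 20%. Under the literal 13.2 there is no shortfall. Section 13.7 also mentions last observation carried forward, which could keep some lost subjects in the analysis.

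On error, the context favours the harmless reading. The sentence on disregarding cases follows one that ties their number to PI training and experience. Section 19.1 has that number determined during training, and roll-ins carry distinct IDs from enrolment. The highest error figures need 24 to 32 evaluable roll-ins and outcome-driven choice. A separate statistical analysis plan may settle the matter.

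Most of this stands as a limit on size: the numerical slip is minor, the power loss is conditional, and 30% is an extreme bound. Carry-forward does not rescue the counts, because 13.1 itself plans on 86 of 108 and 13.2 rules out imputation. Distinct IDs stop a subject being relabelled, but do not say whether that subject is analysed. A plan not supplied cannot be assumed to resolve conflicting protocol text.

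**Conclusion.** The concern holds. The synopsis total of 104 contradicts the 108 in section 13.1, with little effect alone (power 0.891 against 0.914). The 86 evaluable and about 90% power hold with 12 or fewer roll-ins, or if all roll-ins are analysed. They fail if more than 12 are enrolled within 120, excluded, and loss is 20%. The effect is small up to about 2 per site and reaches 64 evaluable and 75% power at the permitted maximum of 40.

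The unresolved inclusion rule is the most consequential part. If disregarding means waiving training cases, error stays at or below 2.6%. If it means dropping treated cases after outcomes, error runs from 2.8% to 6.7% for whole PI sets in the cases tried, and higher only under case-by-case dropping.

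Assumptions: 20% loss applies equally to roll-ins; one PI per site; replacements, which 9.7 to 9.10 allow and 13.2 forbids, count towards the cap. Confidence is high that the texts conflict; whether any choice would be driven by outcomes cannot be known from the documents.

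**What to change.** - In 13.2, state one rule for all roll-ins, fixed before any outcome review: for example, all excluded from the primary analysis and reported separately, or all included.
- In 19.0 and 19.1, delete or clarify the sponsor's option to disregard cases. If it means waiving training cases, say so.
- In the synopsis and 19.1, replace the ambiguous sentence on roll-in data with the rule in 13.2.
- Correct the synopsis to 86 + 22 = 108.
- If roll-ins are excluded, state that at most 12 fit within 120, or restate the evaluable number and power in 13.1 for the permitted maximum (64 and about 75% with 40).
- Count roll-ins per site or per PI throughout.

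The cost is wording in the synopsis, 13.2, 19.0 and 19.1, and in 13.1 if power is restated. No patients are added and the cap stays at 120. The drawback is either fewer roll-ins (12 over 8 sites is 1.5 per site) or a less favourable stated power.

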#### **3.2** Primary Safety Endpoints

Incidence of device related adverse events as defined by perforation, instrument separation, root fracture, sodium hypochlorite accident, or Gutta Percha extrusion, as related to the device for the Treatment Complete cohort.

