## 7.10 Inability to Complete Treatment

If, for any reason, Sonendo GentleWave treatment cannot be completed over the course of no more than two visits, the subject will be considered as a Treatment Incomplete Subject. Subjects in the Treatment Incomplete Cohort will be documented as such but will not be followed for the study. No additional data will be collected on the Treatment Incomplete Cohort. Reasons for incomplete treatment may include, but are not limited to, periodontal issues, uncontrolled bleeding, root fracture, patient reported pain, etc.

These subjects will be counseled by the PI on any treatment they require. Subjects in the Treatment Incomplete Cohort will be responsible for any standard of care treatment.

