## **13.0 STATISTICAL METHODS**

All required data for this study will be collected on paper or electronic Case Report Forms (CRFs). The Investigator (or designated study staff) will assure primary data collection based on source documented dental chart reviews. Independent monitoring will be performed to ensure that the investigator and his/her study team conducted the clinical investigation in accordance with contract specifications, study protocol, Declaration of Helsinki, and applicable local or national regulations, to ensure adequate protection of the rights and safety of subjects and the quality and integrity of the resulting data.

In general, quantitative variables will be summarized to indicate the population sample size (N), number of patients with available data (n), mean, standard deviation, median, minimum, and maximum values. Qualitative variables will be summarized by the population size (N), number of patients with available data (n), number of patients in each category, and the percentage of patients in each category. Analyses will be based on the Safety Population defined as all patients who receive the Sonendo GentleWave System procedure. Details of analysis methods will be described in the statistical analysis plan.

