## 13.6 Safety Analyses

Incidence of device related adverse events as defined by perforation, instrument separation, root fracture, sodium hypochlorite accident or Gutta Percha extrusion, as related to the device will be summarized for the Safety Population.

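### The primary safety endpoint has two stated analysis populations, and the Treatment Complete version could leave out a device-related root fracture that stops treatment

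*Combined protocol and SAP*

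**What the plan says.** Three places tie the primary safety endpoint to completers. The Study Cohorts entry of the synopsis says: "Only subjects in the Treatment Complete cohort will be included in the primary effectiveness and safety endpoint analyses". The synopsis endpoint itself ends: "sodium hypochlorite accident, or Gutta Percha extrusion, as related to the device for the Treatment Complete cohort". Section 3.2 repeats it: "as related to the device for the Treatment Complete cohort".

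The statistical section says something else. Section 13.6 lists the same five events and states that their incidence "as related to the device will be summarized for the Safety Population". Section 13.2 gives the definition: "The Safety Population is defined as all patients who receive the Sonendo GentleWave System procedure". Section 13.0 uses the same definition as the general analysis set ("Analyses will be based on the Safety Population defined as all patients who receive the Sonendo GentleWave System procedure"). Section 13.2 defines the Treatment Complete set separately, as the Efficacy Evaluable population, so the two names are not synonyms.

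Section 13.0 adds: "Details of analysis methods will be described in the statistical analysis plan". Nothing in the supplied document settles the point.

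Section 7.10 makes a subject Treatment Incomplete when GentleWave treatment cannot be finished in at most two visits. The reasons it lists include "periodontal issues, uncontrolled bleeding, root fracture, patient reported pain". It also says that this cohort is not followed and that data collection on it ends.

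**The concern.** A primary endpoint needs one analysis set, fixed in advance. Here two are written down, and the choice between them could be made after the data are seen.

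The two sets also differ in kind. Treatment Complete status is itself a result of treatment, and one endpoint component, root fracture, is among the stated reasons for failing to reach it. A safety rate restricted to completers can therefore exclude a subject because the safety event occurred. At stake is whether such an event counts in the primary incidence or appears only in the adverse event listings. With few expected events, that can be the difference between reporting none and reporting some.

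**Working it through.** **1. Trace one event through the plan.**
- Enrollment and GentleWave treatment both begin when LuxaBite or a Tooth Cap is placed (7.6, 7.7, 7.13, 10.5.1).
- Suppose that a root fracture occurs after that point, is judged device-related, and prevents 100% completion.
- It is an endpoint event by type (synopsis, 3.2, 13.6).
- It is recorded, because adverse events are collected during the procedure and at treatment visits (7.13, 10.3).
- The subject is Treatment Incomplete (synopsis definition, 7.10).
- Under the synopsis and 3.2 the subject is in neither numerator nor denominator. Under 13.6, with receipt of the procedure read as any exposure, the subject is in both.

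**2. Limits of the route.**
- Perforation, or a fracture below the cemento-enamel junction, found before enrollment is a screen failure under either rule (5.4, 7.6.1).
- File shaping precedes enrollment (7.5.4) and counts as traditional therapy (10.5.1).
- Gutta Percha extrusion can only follow obturation, which comes after completion (7.11).
- A fracture that does not prevent completion is counted under both rules.
- A sodium hypochlorite accident could follow the same route, since the device delivers that fluid (2.5.3). That is inference: 7.10 does not list it.

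**3. Inputs for the illustration.** The plan gives no figure for the safety endpoint and no separate number of incomplete subjects. Section 13.1 gives 108 subjects, 86 evaluable, and a 20% allowance that combines loss to follow-up with incomplete treatment. That base reproduces: 86 / (1 - 0.20) = 107.5, rounded up to 108. All event counts below are assumed.

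**4. Formulas.** Let n subjects start treatment, i be incomplete, f be endpoint events among the incomplete and g among completers (at most one per subject).
- Treatment Complete rate = g / (n - i)
- Safety Population rate = (f + g) / n
- The Safety Population rate is the weighted mean of f/i and g/(n - i). So the Treatment Complete rate is the lower one exactly when f/i > g/(n - i).

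Intervals are exact (Clopper-Pearson) 95%. For 0/107 the upper limit is 1 - 0.025^(1/107) = 0.0339. For 1/108 the lower limit is 1 - 0.975^(1/108) = 0.0002 and the upper limit is 0.0505.

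**5. Results with n = 108.**

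| Assumed case | Treatment Complete | Safety Population |
|---|---|---|
| i = 1, f = 1, g = 0 | 0/107 = 0% (0 to 3.4%) | 1/108 = 0.9% (0.02 to 5.1%) |
| i = 22, f = 1, g = 0 | 0/86 = 0% (0 to 4.2%) | 1/108 = 0.9% (0.02 to 5.1%) |
| i = 3, f = 0, g = 2 | 2/105 = 1.90% | 2/108 = 1.85% |

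The second row is an extreme, in which the whole allowance (108 - 86 = 22) is incomplete treatment. The third row shows that the completer rate can also be the higher one. The documents support no event rate, so no probability that the two rules will differ is calculated.

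**The case against.** The strongest reply is that little turns on this. No hypothesis, margin, sample size or stopping rule uses the safety rate; 13.1 sizes the study on healing alone. The statistical section already names the inclusive population, so the remedy is to align three sentences with it. This stands, and it is why the point is not rated higher. It does not remove the conflict: no order of precedence is stated, and the endpoint definition itself names the other set.

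A reader might infer that the plan does drop device-related fractures. The documents do not support that. Section 7.10 does not call the listed fracture device-related, and 7.7.2 names fracture as a possible cause of leakage that halts treatment, so leakage may reveal a fracture that the device did not cause. Only the conditional holds: such an event, if it occurred, could be left out.

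A reader might also infer that safety reporting is suppressed, or that the rate is always biased downwards. Neither follows. Serious events are covered from enrollment (10.6), and reporting of unanticipated device effects has no cohort limit (10.7). The rate can move either way, as the third row of the table shows.

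Finally, the halt to data collection in 7.10 can be read as applying only once a subject is classed as incomplete, which would be compatible with 10.3 and 10.6. That reading is fair, but the plan should state it.

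**Conclusion.** The contradiction is explicit and unresolved. One of the two stated populations is selected on an outcome of treatment and could omit a device-related root fracture that occurs after LuxaBite or Tooth Cap placement and ends treatment. The size of the effect is unknown. The figures of 0% against 0.9% rest on one assumed event among 108 started subjects, with no other incomplete subject and no other endpoint event. They also read receipt of the procedure as covering treatment that was started but not finished, which 13.2 does not spell out.

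The contradiction itself is certain; whether the mechanism would operate in this trial is not. Because the endpoint is descriptive, the rating is should-fix. It rests on a contradictory and selective rule for a primary endpoint, not on a demonstrated bias.

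**What to change.** - **Synopsis (Study Cohorts, Primary Safety Endpoint) and 3.2:** for the primary safety endpoint, replace the Treatment Complete cohort with the Safety Population of 13.6.
- **13.0 and 13.2:** clarify that receiving the procedure means that GentleWave treatment was started (LuxaBite or Tooth Cap placed), whether or not it was completed.
- **13.6:** show the Treatment Complete result as supportive. Give the number of Treatment Incomplete subjects beside the incidence, and note that their follow-up is shorter than the completers' 24 months, so late events are under-ascertained in them.
- **9.7:** this section allows terminated subjects to be left out of the final analysis with no safety exception. State that it does not remove anyone from the safety analysis.
- **7.10 with 10.3, 10.4 and 10.6:** reconcile the end of data collection with the adverse event sections, so that treatment-visit adverse events and the serious events already covered are retained for Treatment Incomplete subjects.
- **Roll-in subjects (synopsis, 19.1):** read literally, the Safety Population includes them, while their data may be left out of the final analysis. State in advance how the safety summary handles them, for example incidence with and without them, rather than excluding them from the Safety Population.

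The cost is wording changes and a few table lines, with no new visits or data collection. The reported incidence may move in either direction.
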